#### **8.6.4 Analyses of secondary efficacy endpoints**

All secondary analyses will be based on the FAS. The analysis based on the PP populations will be performed for the 3 selected efficacy endpoints as specified below.

The change in the secondary endpoints such as serum bile acids, ALT, growth, Albireo PRO and ObsRO sleep parameters will be summarized by visit using descriptive statistics. Change in growth (weight for age and BMI for age) will also be displayed using graphical presentations. The summary of change in the secondary endpoints such as serum bile acids, ALT and growth will also be provided based on the PP analysis set.

Change in serum bile acids, change in ALT, change in growth will also be analyzed using a MMRM model. The model will include terms for baseline, PFIC type, age category, treatment, visit, treatment-by-baseline interaction and treatment-by-visit interaction. Unstructured covariance matrix will be used. The analysis of serum bile acids may be performed based on log transformed values of serum bile acids if deemed appropriate.

The analysis of growth data will be based on calculated values using the software or methods from the Centers for Disease Control and Prevention (CDC) website for patients with age  $\geq 2$  years old and from the WHO website for patients with age  $< 2$  years old. CRF collected growth data will be listed.

The proportion of responders at Weeks 12 and 24 based on the ObsRO instrument will be analyzed using the same model as specified for the primary analysis for EU and RoW. The definition of the responder is a patient who reports a decrease in pruritus score from unrounded baseline equivalent to or greater than the threshold of meaningful change estimated from the blinded psychometric analysis; the results of the blinded psychometric analysis across all anchors support a threshold of a 1.0 point for AM, PM and AM and PM scratching scores. Section 8.9.1 includes more details about the blinded psychometric analysis. Specifically, the averaged pruritus score during weeks 11 and 12 and during weeks 23 and 24 will be used to calculate the proportion of patients achieving meaningful reduction at Week 12 and Week 24 from the baseline score. Similarly, the responder analysis will be conducted based on monthly scores at Week 12 and Week 24. Moreover, the analysis will be performed by AM, PM separately and AM & PM combined. For treatment completers whose last eDiary report day is before Week 24, if there is not enough eDiary data to calculate bi-weekly or monthly average scores at week 24, they will be excluded from analysis.

The proportion of individual assessments meeting the definition of a positive pruritus assessment at the subject level from Weeks 0-4, Weeks 0-8, Weeks 0-12, Weeks 0-18, Weeks 0-24, respectively, and the proportion of positive pruritus assessments at each 4-week interval over the 24-week treatment period for AM or PM, respectively will be analyzed using the same model as specified for the primary analysis for US. This analysis will be performed for PRO/ObsRO instruments separately.

The number and percent of patients achieving positive pruritus assessment for more than 50% of the time will be summarized by treatment group. Both AM and PM pruritus assessments will be included in the analysis of this endpoint. The proportion of patients achieving positive pruritus assessment for more than 50% of the time will be analyzed using the same model as specified for the primary analysis for EU and RoW. This analysis will also be performed separately for AM pruritus assessments only and PM pruritus assessments only.

A cumulative distribution function (CDF) plot showing proportions of patients achieving positive pruritus assessment for more than X% of the time, for X from 0 to 100%, by treatment group will be provided.

Number and percent of patients undergoing biliary diversion surgery and/or liver transplant will be summarized by using descriptive statistics. Kaplan-Meier curves will be used when appropriate for time to event data. Median event-free times and associated 95% confidence intervals will be calculated for each treatment group using Brookmeyer and Crowley methodology and a log-log transformation for constructing confidence intervals.

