### **2.2 Secondary objectives**

- To evaluate the effect of odevixibat on serum alanine aminotransferase (ALT) concentration
- To evaluate the effect of odevixibat on growth
- To evaluate the effect of odevixibat on sleep disturbance
- To evaluate the effect of odevixibat on the need for surgical treatment (biliary diversion or liver transplantation)
- To assess the safety and tolerability of repeated daily doses of odevixibat for 24 weeks

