### 4.2 Secondary efficacy endpoints

The secondary efficacy endpoints include the following:

- **EU and RoW:** Proportion of positive pruritus assessments at the subject level over the 24-week Treatment Period based on the Albireo ObsRO instrument.
- **US:** Proportion of patients experiencing at least a 70% reduction in fasting s-BA concentration from baseline to the end of treatment or reaching a level  $\leq 70$   $\mu\text{mol/L}$  compared to placebo after 24 weeks of treatment.

- **All Regions:**

All other secondary endpoints are compared to placebo.

- Change from baseline to Week 12 and to Week 24 in fasting s-BA
- Change from baseline to Week 12 and to Week 24 in serum ALT concentration
- Change in growth from baseline to Week 12 and to Week 24, defined as the linear deficit (height for age, weight for age and MBI for age) compared to a standard growth curve (Z-score, SD from P50)
- Proportion of responders for pruritus scores at Weeks 12 and 24 based on the ObsRO instrument. For pruritus scores, a responder is defined as a patient achieving a reduction in score equivalent to or exceeding the clinically meaningful threshold established from the blinded psychometric analysis (Pruritus Evidence Dossier).
- Change in sleep parameters measured with the Albireo PRO and ObsRO instruments by each 4-week interval over the 24-week treatment period
- Proportion of individual assessments meeting the definition of a positive pruritus assessment at the subject level over the 24-week treatment period as reported on the Albireo PRO instrument. A positive pruritus assessment includes an itch score  $\leq 1$ , or at least a one-point drop from baseline based on the Albireo PRO instrument; only patients  $\geq 8$  years of age will complete the Albireo PRO instrument
- Proportion of individual assessments meeting the definition of a positive pruritus assessment at the subject level from Weeks 0-4, Weeks 0-8, Weeks 0-12, Weeks 0-18, Weeks 0-24, respectively, and the proportion of positive pruritus assessments at each 4-week interval as reported on the Albireo ObsRO instrument. A positive pruritus assessment is defined as a scratching score of  $\leq 1$  or at least a one-point drop from baseline on the Albireo ObsRO instrument. At each assessment, the AM or PM score will be compared to the baseline AM or PM average, respectively.

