## 8 STATISTICAL METHODS

### 8.1 General statistical conventions

All personnel involved with the analysis of the study will remain blinded until database lock. For DSMB analyses see Section 8.9.2. All statistical procedures will be completed using SAS® version 9.4 or higher.

Statistical testing for each primary endpoint analysis will be performed with a 1-sided overall Type I error rate of 0.025, adjusting for 2 comparisons between each active arm vs. the control. All other secondary endpoints for treatment comparisons will not be adjusted for multiplicity and nominal p values will be provided. Two-sided 95% confidence intervals (CI) will be provided when relevant.

For analysis adjusting for stratification factors (PFIC type and age category), if a patient is under 6 months due to imputed birth date ([Appendix A](#)), then the patient will be grouped to the age category ‘6 months to 5 years’.

Continuous variables will be summarized using descriptive statistics, including the number of patients with non-missing value (n), mean, median, SD, minimum and maximum. “n” will be presented without a decimal point, minimum and maximum values will be presented in the same precision as in the database, mean and median will be presented in one more decimal place than the minimum and maximum, and SD will be presented in one more decimal place than the mean and median.

For categorical variables, summaries will include counts of patients (frequencies) and percentages. Percentages will be rounded to one decimal place. Descriptive summaries of change from baseline in categorical variables will be provided using shift tables, if applicable.

For summary purposes, if not otherwise specified, the baseline value of a parameter is defined as the last non-missing assessment of that parameter prior to the first intake of study drug ([Appendix A](#)). Derived variables used for the analyses are provided in [Appendix A](#). All summaries will be presented by treatment group, unless otherwise specified.

For summary tables, the following 2 presentations will be used:

- For baseline related tables and protocol deviations: odevixibat 40 µg/kg/day, odevixibat 120 µg/kg/day, odevixibat 2 doses combined, placebo, and overall (3 treatment groups combined) will be presented.
- For the safety and efficacy related tables: odevixibat 40 µg/kg/day, odevixibat 120 µg/kg/day, odevixibat 2 doses combined, and placebo will be presented.

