### 2. Efficacy Analyses

#### (a) Changed the definition of fasting s-BA baseline

**Protocol:** Fasting s-BA baseline will be calculated as the average of the value at randomization and the previous visit (Clinic Visit 2).

**SAP:** Fasting s-BA baseline will be calculated as the average of the last 2 values prior to the first dose. The reason to change is that some patients may have unscheduled assessments between Clinic Visit 2 and Randomization Visit.

(b) Added the details of strata pooling strategy for the CMH test

(c) Added rounded baseline score which will be used for the analysis of pruritus assessments

(d) Added analyses for the number of patients achieving positive pruritus assessment for more than 50% of the time during 24-week treatment period

(f) Added the following analyses for the US primary endpoint of pruritus assessments

- An additional method to calculate the proportion of positive pruritus assessments up to the last report day before or on Day 168. In other words, the denominator to calculate the proportion will be (the last report day x 2). All missing data before or on the last report day will be considered as negative assessments.
- Additional supportive analysis will exclude patients from the primary endpoint analysis who have a baseline AM or baseline PM average score that rounded to 0 or 1.
- Multiple imputation and tipping point analysis for pruritus assessments as a continuous endpoint.

(g) Added the following analyses for the EU and RoW primary endpoint of fasting s-BA responder endpoint

- Tipping point analysis to evaluate the influence of missing data at the end of treatment

(h) Added the following analysis for secondary endpoints

- Change in serum bile acids, change in ALT, change in growth will be analyzed using a MMRM model

(i) Changes in Subgroup Analysis

- Removed a subgroup: for patients who were not included in the previous Study [A4250-003](#)
- Added subgroups by region (US, EU and RoW), sex, race, ethnicity, baseline serum bile acid ( $\geq 250$  and  $< 250$   $\mu\text{mol/L}$ ), Child-Pugh classification, Bile Salt Export Pump (BSEP) type of PFIC 2 patients, and the use of UDCA, rifampicin (alone or either one). Subgroup analyses may be conducted for hepatic impairment classification per NCI Organ Dysfunction Working Group (ODWG) if appropriate.

(j) Corrected Formula of PELD Score and APRI Score

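### Section 4.2 says change in sleep parameters is compared to placebo, but Section 8.6.4 plans only descriptive summaries for sleep, with no between-arm estimate, interval or p-value

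*SAP*

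**What the plan says.** SAP Section 2.2 lists as a secondary objective: "To evaluate the effect of odevixibat on sleep disturbance". Section 4.2, under the heading for all regions, opens with "All other secondary endpoints are compared to placebo". The list below it includes "Change in sleep parameters measured with the Albireo PRO and ObsRO instruments by each 4-week interval over the 24-week treatment period".

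Section 8.6.4 then sets out the analyses. Serum bile acids, ALT, growth and sleep are grouped in one descriptive sentence, which ends: "ALT, growth, Albireo PRO and ObsRO sleep parameters will be summarized by visit using descriptive statistics". The model-based analysis follows two sentences later: "Change in serum bile acids, change in ALT, change in growth will also be analyzed using a MMRM model". Its terms are baseline, PFIC type, age category, treatment, visit, and the treatment-by-baseline and treatment-by-visit interactions, with an unstructured covariance matrix. Section 9, item 2(h), repeats the scope of that model: "Change in serum bile acids, change in ALT, change in growth will be analyzed using a MMRM model".

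On layout, Section 8.1 states: "All summaries will be presented by treatment group, unless otherwise specified". It fixes four columns for efficacy tables: each dose, the two doses combined, and placebo. It also says that nominal p-values will be provided for secondary treatment comparisons.

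**The concern.** Four continuous secondary endpoints enter Section 8.6.4 together and three leave with a model. The one dropped is tied to its own secondary objective and sits in the list that Section 4.2 says is compared with placebo. A programmer following Section 8.6.4 literally would produce tables of sleep scores and changes by arm, and nothing that estimates a dose-versus-placebo difference with its uncertainty.

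Two things are at stake. First, a reader of the study report would have to judge the sleep effect by eye, from arm means and SDs. Second, if someone later supplies the p-value that Sections 4.2 and 8.1 lead one to expect, the sleep item, time interval, model and handling of missing diary days would be chosen outside the SAP, possibly after unblinding.

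**Working it through.** The SAP states no figure for sleep, so there is none to reproduce. The check is a reading of every place where a sleep comparison could be specified.

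1. **Section 8.6.4, descriptive sentence.** Sleep is included: "Albireo PRO and ObsRO sleep parameters will be summarized by visit using descriptive statistics". The open-ended wording that introduces examples belongs to this sentence only.
2. **Section 8.6.4, MMRM sentence.** Serum bile acids, ALT and growth are named. The list is closed and sleep is absent.
3. **Section 8.6.4, remaining paragraphs.** The pruritus responder and more-than-50%-of-the-time endpoints take the s-BA primary model (CMH). The proportions of positive assessments take the pruritus primary model (ANCOVA). Surgery is descriptive, with Kaplan-Meier curves. None of these covers sleep.
4. **Section 8.6.5.** The additional sleep parameters, which are exploratory, are analysed descriptively. By contrast PedsQL, also exploratory, gets an ANCOVA between treatment groups.
5. **Section 8.8.** Sleep is not among the subgroup parameters.
6. **Section 9, item 2(h).** The same three MMRM endpoints appear.
7. **Appendix E.** The code covers the CMH test and the ANCOVA for the proportion of positive pruritus assessments. There is no sleep model.
8. **Sections 8.1 and 8.6.1.3.** These are general rules on nominal p-values, confidence intervals and multiplicity. They name no method for sleep.

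Result: descriptive statistics are specified for sleep; a between-arm estimate, confidence interval or test is not.

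Next, whether the data would support a model. Appendix A derives sleep scores in the same way as the AM and PM scratching scores, noting one rating per day, and this includes 28-day averages with a rule for missing entries. Appendix B applies the diary windows to sleep and gives six 4-week windows, Week 4 to Week 24. The inputs for a repeated-measures model therefore already exist. An unstructured covariance over six intervals has 6 × 7 / 2 = 21 parameters. That is a lot for arms of about 20 patients, and more so for the patient-reported items, which only patients aged 8 or over complete.

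Two smaller mismatches surfaced. Section 4.2 defines the endpoint by 4-week interval, while Section 8.6.4 summarises by visit. Section 4.2 also does not name the secondary sleep parameters. Section 4.3 makes additional ones exploratory, with tiredness and number of awakenings as examples, whereas Appendix A lists those together with difficulty falling and staying asleep.

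**The case against.** The strongest reply is that placebo is not absent from the sleep output. Section 8.1 puts both doses, the combined doses and placebo in adjacent columns, and Section 8.6 plans figures by treatment group and visit for selected efficacy endpoints, citing other patient- and caregiver-reported outcomes as examples. This stands. A reader might infer that sleep would be reported only as isolated within-arm changes, or that the trial cannot address its sleep objective at all. The documents support neither: the concurrent placebo change is on display, and only formal inference is missing.

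A second reply is that comparison with placebo does not always mean a test in this SAP. Surgery is in the same Section 4.2 list and is also handled descriptively. Section 8.6.1.3 calls the secondary analyses supportive, and the nominal p-value rule in Section 8.1 can be read as applying only where a comparison is specified. The fault might then be one loose sentence in Section 4.2. That is possible, and it is why the fix offers two routes. It does not remove the disagreement: few surgical events could explain a descriptive approach there, whereas sleep is recorded daily and its monthly scores are already derived.

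A third reply is that the protocol may specify a method. It is not at hand, and the SAP points to none for sleep. For the same reason, sleep's absence from the Section 9 list of changes is weak evidence and is not relied on here.

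Two other tempting arguments should be left aside. One is to calculate how often a within-arm interval would exclude zero without any drug effect. Section 8.1 defines the continuous summaries as n, mean, median, SD, minimum and maximum, so no such interval is planned for sleep. The other is to describe sleep as twice-daily data, when Appendix A says there is one rating per day.

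**Conclusion.** The point holds as an inconsistency within the SAP. Section 4.2 promises a comparison with placebo for sleep, Section 8.6.4 specifies only descriptive summaries, and no other section closes the gap. The consequence is confined to one secondary objective, which has no prespecified between-arm estimate, confidence interval or nominal p-value. Both primary analyses, the sample size and the closed testing procedure are untouched.

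No numerical size is attached. The SAP gives no sleep effect size or SD, and borrowing the pruritus effect size would measure a different outcome. The conclusion rests on the SAP text alone and on reading the MMRM list as closed. It should be corrected, because a named objective is affected and the remedy is small.

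**What to change.** In Section 8.6.4, add change in the secondary Albireo ObsRO and PRO sleep parameters to the MMRM sentence, and specify the following:

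- **Parameters.** Name the secondary sleep parameters. Keep those that Section 4.3 makes exploratory, such as tiredness and number of awakenings, descriptive.
- **Outcome and model.** Use the six 4-week averages from Appendices A and B with the model terms already stated, replacing visit by 4-week interval. This also removes the interval-versus-visit mismatch.
- **Reporting.** Give each dose, and the pooled doses, versus placebo as LS mean difference, 95% CI and nominal p-value.
- **Fallbacks.** State a simpler covariance structure if the unstructured one does not converge. Set a minimum sample size for the PRO model, as Section 8.6.5 does for child-reported PedsQL, where no ANCOVA is run with fewer than 10 patients.
- **Section 9.** Update the list of changes only if this differs from the protocol.

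The cost is a few lines of SAP text and one further set of tables on variables already derived. The small downside is more unadjusted nominal p-values, which Section 8.1 already accepts for secondary endpoints.

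If the sponsor intends sleep to be descriptive only, the alternative is to say so in Section 4.2 by excepting sleep from the statement on comparison with placebo. Either way, the two sections need to agree before the database is locked and unblinded.

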### 8.6.5 Analyses of exploratory endpoints

The exploratory efficacy variables are listed in Section 4.3. All the exploratory analyses will be based on the FAS.

Exploratory variables including Global Symptom Relief, biochemical markers and measures of bile acid synthesis, Albireo PRO and ObsRO itching/scratching severity scores, additional Albireo PRO and ObsRO sleep parameters, PELD/MELD score, APRI score, and the Fib-4 score will be analyzed descriptively for categorical and continuous data. For continuous data, the change from baseline will be analyzed in addition to the presentation of actual visit values. For Albireo PRO and ObsRO itching/scratching severity scores, unrounded baseline will be used to calculate change from baseline. For categorical data, shift tables or frequency and percentages of patients will be presented as appropriate. A line graph of itching/scratching daily severity scores of Albireo PRO and ObsRO over time for each patient will be provided.

For continuous data, such as PELD/MELD score, APRI score, and Fib-4 score, biochemical markers and measures of bile acid synthesis, the change from baseline to Week 24 will be analyzed descriptively in addition to the actual visit values. Global Symptom Relief data at Weeks 4, 12, and 24 will be summarized as categorical variables. Time points (visit window) are specified in [Appendix B](#).

Comparisons of the change from baseline at Week 24 in the PedsQL total score (calculated as average score of all answered items) between the treatment groups will be conducted using analysis of covariance (ANCOVA). The model will include terms for baseline, PFIC type, age category, and treatment. The analysis will be conducted based on the total scores reported by child ( $\geq 5$  years of age) and by parent (only including patients  $\geq 5$  years of age) separately. If the sample size based on child reported data ( $\geq 5$  years of age) is less than 10, then ANCOVA will not be conducted. The PedsQL total score of the family impact module will be analyzed similarly. The total score and the domain scores will be summarized descriptively.

Change from baseline to Week 24 in stage of liver fibrosis measured by Fibroscan® will be analyzed descriptively. The frequencies of stages may be summarized by shift tables. Steatosis grade analysis will be performed in a similar fashion.

### 8.6.6 Analyses based on exit survey data

The exit survey in [Appendix F](#) contains 3 questions and will be done by patients and caregivers separately. The answer Yes in Questions 1 and 2 will be verified with Question 3 for a positive and meaningful change.

The exit survey has the following questions:

1. Have you or your child experienced change from the study drug at the end of the study?  
Yes/No;

2. Was the change meaningful? Yes/No;

3. In what way was the change meaningful?

The exit survey was implemented in the middle of the trial so data from the exit survey will not be available for all patients. Analyses on exit survey are listed below. Analyses will be repeated considering missing data as No to Questions 1 and 2, and considering missing data as Yes to Questions 1 and 2.

The number and percent of patients with the following categories will be provided by treatment and overall:

- Q1 answer=Yes and Q2 answer=Yes
- Q1 answer=No and Q2 answer=No
- Q1 answer=Yes and Q2 answer=No

The exit surveys will be answered by both patients ( $\geq 8$  yrs) and caregivers. Exit survey data will be provided in a data listing.

The following analyses on the exit survey will be performed using the descriptive summary based on pruritus assessments of Albireo ObsRO instrument in the last 2 weeks while patients are still on the study medications.

- For patients who answered Yes to Questions 1 and 2 in the exit survey, changes from baseline in the average scratching score based on the Albireo ObsRO instrument in the last 2 weeks before treatment termination
- For patients who answered No to Questions 1 or 2 in the exit survey, changes from baseline in the average scratching score based on the Albireo ObsRO instrument in the last 2 weeks before treatment termination

The summary based on the pruritus assessments of Albireo PRO instrument will also be provided.

